CLINICAL STUDY PROTOCOL

PHASE 1, OPEN-LABEL, DOSE ESCALATION STUDY OF DS-3032B, AN ORAL MDM2 INHIBITOR, TO ASSESS SAFETY, TOLERABILITY AND PHARMACOKINETICS IN JAPANESE PATIENTS WITH RELAPSED OR REFRACTORY ACUTE MYELOID LEUKEMIA

DS3032-A-J104

VERSION 01.4, 07 OCT 2019

DAIICHI SANKYO

CONFIDENTIALITY STATEMENT

Information contained in this document is proprietary to Daiichi Sankyo Co., Ltd. The information is provided to you in confidence which is requested under an agreed upon and signed Confidentiality and Disclosure Agreement. Do not give this document or any copy of it or reveal any proprietary information contained in it to any third party (other than those in your organization who are assisting you in this work and are bound by the Confidentiality and Disclosure Agreement) without the prior written permission of an authorized representative of Daiichi Sankyo Co., Ltd.

PROTOCOL SYNOPSIS

Protocol Number:	DS3032-A-J104
Investigational Substance Code:	DS-3032b
Generic Name/INN:	milademetan
Study Title:	Phase 1, open-label, dose escalation study of DS-3032b, an oral MDM2 inhibitor, to assess safety, tolerability and pharmacokinetics in Japanese patients with relapsed or refractory acute myeloid leukemia
Study Phase:	Phase 1
Indication Under Investigation:	Acute myeloid leukemia (AML)
Study Objectives:	
Primary objective:
 
To evaluate the safety and tolerability of DS-3032b monotherapy administered as multiple doses and assess the maximum tolerated dose (MTD) in Japanese subjects with relapsed or refractory AML.
 
Secondary objectives:
 
• To evaluate the pharmacokinetics of DS-3032a• To exploratively evaluate the antitumor effect of DS-3032b 
Type of study objectives:
 
Efficacy, safety, pharmacodynamics, pharmacokinetics, tolerability, pharmacogenomics

Study Design:	
Type of study: Interventional
 
Type of intervention: Pharmaceutical drugs
 
Type of proposed indications: Treatment
 
Study design: Single arm

Dose finding method:	An optimal dose of DS-3032b will be explored from among four doses (Subtrials A, B, C, and D) based on the fixed dosing schedule. The study will be started from Subtrial A, and other subtrials will be conducted as necessary. Explorative assessment of MTD in each subtrial will be guided by a modified continual reassessment method (mCRM) using a Bayesian logistic regression model (BLRM) incorporating the escalation with overdose control (EWOC) principle.

Combinations of Doses and Dosing Schedules

Dose (mg)	Subtrial C	Subtrial B	Subtrial A	Subtrial D
	C-3	B-3	A-3	D-3
	C-2	B-2	A-2	D-2
	C-1	B-1	A-1	D-1
	3/14 × 2	7/28	14/28	21/28
	Dosing schedule (day/day)			

Level of blinding: Open-label

Type and presence/absence of comparator: Not applicable

Add-on to standard therapy: None

Study Duration:	06 Jul 2018 to 31 Dec 2019
Location:	Japan
Study Centers:	Refer to Attachment 2.
Planned Sample Size:	9 to 24 subjects
Study Population (Inclusion and Exclusion Criteria)	
Inclusion criteria
 
1. Provision of written informed consent for participation in this study.2. Age \geq20 years old upon enrollment in this study.3. Having AML (including those with a history of myelodysplastic syndrome [MDS]) satisfying either of the following:
• Have failed to achieve remission with at least 1 cycle of prior induction therapy• Have relapsed after achieving remission with prior therapy4. Those who appear unable to achieve persistent remission with standard treatment, who failed to complete potentially curative treatment, or who have no treatment options with expected therapeutic efficacy.5. Eastern Cooperative Oncology Group (ECOG) performance status (PS) of 0 to 2 (refer to “Appendix 2”).6. Having laboratory data satisfying all of the following criteria in the measurement within 14 days before enrollment in this study.

Laboratory Parameter	Requirement
AST	$\leq 2.5 \times$ the upper limit of normal of the center (ULN)
ALT	$\leq 2.5 \times$ ULN
Total bilirubin	$\leq 1.5 \times$ ULN
Serum creatinine	Creatinine clearance ≥ 60 mL/min, as calculated using the modified Cockcroft Gault equation*
	In case of creatinine clearance ≥ 50 mL/min and <60 mL/min, as calculated using the above equation, the subject may be enrolled if the serum creatinine level is $\leq 1.5 \times$ ULN.
Prothrombin time-international normalized ratio (PT-INR)	$\leq 1.5 \times$ ULN
Activated partial thromboplastin time (aPTT)	$\leq 1.5 \times$ ULN

*: $([140 - \text{age (year)}] \times [\text{actual weight (kg)}]) / [72 \times \text{serum creatinine (mg/dL)}] (\times 0.85 \text{ [if female]})$

7. Able to take the following interval during the period from the last dose or last procedure of prior therapy to the start day of treatment with the study drug (study treatment) in this study.
 - Cytotoxic drugs: 2 weeks (48 hours for hydroxycarbamide used for the purpose of controlling the increase in white blood cells)
 - Non-cytotoxic drugs: At least 5 times the half-life of the drug
8. Women of childbearing potential must have a negative pregnancy test at screening and must be willing to use highly effective birth control (eg, barrier contraceptives with spermicides, intrauterine device) during the following period: Upon enrollment, during the treatment period, and for at least 95 days after the last dose of DS-3032b.
Women of childbearing potential are those in the period from first menstruation to menopause (no menstrual period for a minimum of 12 months). This, however, shall exclude permanently (surgically) sterile women.
9. Males must be surgically sterile or willing to use highly effective birth control upon enrollment, during the treatment period, and for at least 95 days after the last dose of DS-3032b. Male subjects may not donate their sperm during the study period and for at least 95 days after the last dose of DS-3032b.
10. Able to be hospitalized during the dose-limiting toxicity (DLT) evaluation period.


Study Population (Inclusion and Exclusion Criteria)
	
Exclusion criteria
 
1. Diagnosis of acute promyelocytic leukemia.2. Chronic myeloid leukemia in blast crisis (positive for a breakpoint cluster region- c-Abelson [BCR-ABL] fusion gene).3. History of or concurrent central nervous system leukemia.4. History of hematopoietic stem cell transplant (HSCT) and meeting any of the following:
• Transplantation within 60 days before the start of study treatment• Persistent graft-versus-host disease (GVHD) that is clinically significant, requires the start of treatment, or requires intensification of treatment within 21 days before informed consent• Persistent Grade ≥ 2 clinically significant or irreversible non-hematological toxicity related to transplantation5. Uncontrolled infection requiring intravenous antibiotics, antifungals, or antivirals.6. A positive test result for hepatitis C virus (HCV) antibody or human immunodeficiency virus (HIV) antibody within 90 days before enrollment.7. A positive test result for hepatitis B surface (HBs) antigen within 90 days before enrollment.8. A positive test result for hepatitis B core (HBc) antibody or HBs antibody with hepatitis B virus (HBV)-DNA levels ≥ 2.1 log copies/mL, despite a negative test result for HBs antigen, within 90 days before enrollment.9. Receiving strong cytochrome P450 (CYP) 3A inhibitors within 7 days before the start of study treatment.10. Receiving strong CYP3A inducers within 14 days before the start of study treatment.11. History of or current cardiovascular disease as specified below:
• QT corrected for heart rate using Fridericia's method (QTcF) interval >450 ms, determined as the average of triplicate electrocardiogram (ECG) measurements taken within 14 days before enrollment in this study• Class III or more severe congestive heart failure according to "Appendix 3 New York Heart Association (NYHA) Functional Classification" within 6 months before enrollment in this study• History of myocardial infarction within 6 months before enrollment in this study• History of angina pectoris attack within 6 months before enrollment in this study
--	---

- History of arrhythmia requiring treatment within 6 months before enrollment in this study
- Need for a pacemaker or implantable cardioverter defibrillator
- Diagnosed or suspected congenital long QT syndrome
- History of life-threatening ventricular arrhythmia (ventricular tachycardia, ventricular fibrillation, or torsades de pointes)
- History of bradyarrhythmia (eg, atrioventricular block)
- Clinically significant electrolyte abnormalities that can induce secondary long QT syndrome
- Uncontrolled hypertension despite pharmacotherapy etc.

12. Adverse drug reactions (excluding alopecia) to previous therapy (treatment for AML and/or anticancer therapy), which have not resolved or returned to Grade 1 or baseline. Patients with chronic Grade 2 adverse drug reactions (eg, chemotherapy-induced neuropathy) may be eligible when the investigator or subinvestigator decides that there are no clinical safety concerns from the standpoint of the patient's safety.

* The grade will be assessed according to the "Common Terminology Criteria for Adverse Events (CTCAE) Version 5.0."

13. History of another malignant tumor requiring treatment within 2 years before enrollment in this study. However, patients whose disease is considered to have been cured by local treatment (eg, non-melanoma skin cancer, superficial bladder cancer, or carcinoma in situ of the cervix or breast) may be eligible for participation in the study.

14. Predisposition to serious infection (eg, cystic fibrosis, congenital or acquired immunologic disease, hemorrhagic disease, or cytopenia unrelated to AML).

15. Disseminated intravascular coagulation or other clinically significant coagulation abnormalities.

16. Extensive surgery within 28 days before the start of study treatment.

17. Radiation therapy within 28 days before the start of study treatment.

18. Any factor that could preclude adequate absorption of DS-3032b (eg, refractory nausea and vomiting, malabsorption, biliary shunt, significant bowel resection, and/or GVHD affecting the gut).

19. Pregnant or breastfeeding women.

20. Patients who are otherwise considered ineligible for the study in the opinion of the investigator or subinvestigator.

Study Drug(s):

Dose:

The starting dose of DS-3032b in Subtrial A will be 90 mg. The subsequent doses will be determined, taking the following into consideration.

- i) Recommended dose, guided by mCRM using a BLRM incorporating the EWOC principle
- ii) Clinical evaluation of the toxicological profile and information on pharmacokinetics/pharmacodynamics (PK/PDy)

Dose increments should be at least 1.3-fold in order to make a distinction among the dose cohorts, considering inter-subject variability in exposure. Even if the recommended dose for the next cohort calculated by the model is more than 2-fold, the dose should be no more than 2-fold.

Regimen:

In Subtrial A, the study drug will be administered on Days 1 to 14, followed by a 14-day rest, in a 28-day cycle (14/28 schedule). Each cycle is 28 days long. The study treatment will be continued in 28-day cycles until any of the withdrawal criteria apply. Assessment of the other dosing schedules (Subtrials B, C, and D) will be conducted if it becomes necessary to evaluate the safety of DS-3032b. Dosing schedules in each subtrial are shown in the table below.

Subtrial A	14-day treatment	14-day drug rest		
Subtrial B	7-day treatment	21-day drug rest		
Subtrial C	3-day treatment	11-day drug rest	3-day treatment	11-day drug rest
Subtrial D	21-day treatment		7-day drug rest	

(in a 28-day cycle)

Capsules with two different strengths will be used as the study drug (30 mg and 100 mg). The study drug will be orally taken once daily (qd). Meal consumption should be avoided from 2 hours before dosing to 1 hour after dosing.

Prohibited concomitant drugs and therapies, and restricted concomitant drugs:

Prohibited concomitant drugs and therapies:

- From informed consent to the day of the Follow-up:
Anticancer treatment other than the study drug (excluding hydroxycarbamide), other investigational products, and investigational medical devices

- From 14 days before the start of study treatment to the day of the Follow-up:
Strong CYP3A inducers and St. John's wort-containing foods and supplements
- From 7 days before the start of study treatment to the day of the Follow-up:
Strong CYP3A inhibitors and grapefruit-containing foods and beverages

Restricted concomitant drugs:

- Hydroxycarbamide should be used as per the following instructions.
Use of hydroxycarbamide is prohibited during the period from 48 hours before treatment with DS-3032b to the start of treatment with DS-3032b. It is, however, allowed to concomitantly use hydroxycarbamide to control white blood cell counts at doses up to 5 g/day for a total of 8 days or less only during the period from after the start of treatment with DS-3032b to the end of the Follow-up.
- Prophylactic treatment for the following symptom is prohibited during the DLT evaluation period. However, treatment given as supportive care for the following symptom is allowed.
Neutropenia: Granulocyte colony stimulating factor (G-CSF) products etc.

Study procedures:	Refer to Appendix 1 .
Study Endpoints:	
Safety endpoints:
 
Adverse events (AE), ECOG PS, laboratory data, body weight, vital signs, and 12-lead ECG

	
Efficacy endpoints:
 
Complete remission (CR), CR with incomplete hematological recovery (CRi), CR with partial hematological recovery (CRh), partial remission (PR), morphologic leukemia-free state (MLFS), stable disease (SD), progressive disease (PD), composite CR (CRc) rate (CR + CRi + CRh), response rate (CRc + PR), and duration of CRc

Pharmacokinetic endpoints:

Plasma DS-3032a concentration and pharmacokinetic parameters (Subtrial A)

C1D1 (Cycle 1 Day 1): Cmax, Tmax, AUClast, AUC8h, AUC24h, AUCinf*, Kel*, t1/2*, CL/F*, Vz/F*

C1D14 (Cycle 1 Day 14)**: Cmax, Ctrough, Cavg, Tmax, AUC8h, AUC24h, Kel*, t1/2*, CLss/F***, Vz/F****, AR

*: To be calculated only if possible.

**: To be read as C1D7 (Cycle 1 Day 7) in Subtrial B, C1D3 (Cycle 1 Day 3) in Subtrial C, and C1D15 (Day 15) in Subtrial D.

***: Not to be calculated because steady state will not be reached in Subtrial C.

Pharmacodynamic endpoints:

Tumor protein p53 gene (*TP53*) mutation and serum macrophage inhibitory cytokine-1 (MIC-1) level

Primary statistical analyses:

Safety analyses:

The DLT rate will be estimated for each dose using mCRM based on DLT evaluation data of all evaluable subjects, and the MTD will then be determined. AEs that occur or worsen after the start of study treatment will be summarized in frequency tables by event, causality with the study drug, and grade according to the CTCAE. For laboratory data, vital signs, body weight, and 12-lead ECGs, a frequency table or shift table will be prepared for categorical data and summary statistics will be calculated for quantitative data. Also, frequency table(s) with detailed descriptions of DLTs (if any) will be prepared.

Efficacy analyses:

Frequency tables will be prepared for best response. The CRc rate, response rate, and transplantation rate will be calculated. Summary statistics will be calculated for the duration of CRc.

Pharmacokinetic analyses:

Pharmacokinetics will be analyzed for each subtrial. Summary statistics of plasma concentrations of DS-3032a will be calculated by dose at each time point, and a plasma concentration-time profile will be prepared.

For the pharmacokinetic parameters that are calculated by the non-compartmental analysis, summary statistics will be calculated by dose.

Pharmacodynamic analyses:

For PDy values and PDy parameters, summary statistics will be calculated by treatment group.

Adaptive design: Present

Withdrawal Criteria of the Study:

Subjects will be withdrawn from the study for the following reasons.

1. Apparent progression of the disease is found.
2. It becomes difficult to continue the study treatment due to

AEs (refer to “Section 5.5 Actions to be Taken for Adverse Events”).

3. A *TP53* mutation is detected after study treatment and it is decided inappropriate to continue the study for the subject.
4. The subject is found to be ineligible for the study after enrollment in the study.
5. The subject withdraws his/her consent to participation in the study.
6. The sponsor decides to prematurely terminate the study.
7. The subject has received the study drug on less than 75% of the specified number of dosing days in Cycle 1.
8. Other cases that the investigator or subinvestigator judges it inappropriate to continue the study for the subject.

TABLE OF CONTENTS

PROTOCOL SYNOPSIS	2
TABLE OF CONTENTS.....	11
LIST OF TABLES	17
LIST OF FIGURES	18
LIST OF ABBREVIATIONS AND DEFINITIONS OF TERMS.....	19
LIST OF ABBREVIATIONS.....	19
LIST OF PHARMACOKINETIC PARAMETERS.....	21
LIST OF TERMS.....	22
1. INTRODUCTION	23
1.1. Background of This Study	23
1.2. Summary of Significant Findings Obtained from Nonclinical Studies	24
1.2.1. Pharmacology.....	24
1.2.2. Safety Pharmacology	25
1.2.3. Pharmacokinetics and Drug Metabolism	26
1.2.4. Toxicology	27
1.3. Summary of Significant Findings Obtained from Previous Clinical Studies	28
1.3.1. Overseas Phase 1 Studies (Study DS3032-A-U101 and Study DS3032-A-U102).....	28
1.3.2. Japanese Phase 1 Study (Study DS3032-A-J103).....	29
1.4. Known and Foreseeable Risks	30
2. STUDY OBJECTIVES.....	32
3. STUDY DESIGN.....	33
3.1. Starting Dose in Each Subtrial	33
3.2. Explorative Dose Finding in Each Subtrial.....	34
4. STUDY POPULATION	35
4.1. Selection of Subjects	35
4.1.1. Inclusion Criteria.....	35
4.1.2. Exclusion Criteria	36
4.1.3. Registration of Subjects	39
4.1.3.1. Flow of Subject Registration.....	39

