3. STUDY DESIGN

This is a Phase 1, multicenter, open-label uncontrolled study. Combinations of doses and dosing schedules are shown in “[Figure 3.1 Combinations of Doses and Dosing Schedules](#).” Four dose-finding Subtrials (Subtrials A, B, C, and D) of DS-3032b will be conducted by fixing the dosing schedule. The study will be started from Subtrial A, and other subtrials will be conducted as necessary.

In Subtrials A, B, and D, the study drug will be administered once daily (qd) on Days 1 to 14, Days 1 to 7, and Days 1 to 21, followed by a 14-day, 21-day, and 7-day rest, respectively, in a 28-day cycle. In Subtrial C, the study drug will be administered once daily (qd) on Days 1 to 3, followed by a 11-day rest, in a 14-day subcycle, which will be repeated twice in a 28-day cycle.

Subjects must be hospitalized in Cycle 1, which is the DLT evaluation period. The number of treatment cycles will not be specified, and the study treatment for each subject will be continued unless the criteria provided in “[Section 5.6 Withdrawal Criteria](#)” are met.

The MTD will be determined for each subtrial (see “[Section 5.3.2 Definition of Maximum Tolerated Dose](#)”).

Figure 3.1: Combinations of Doses and Dosing Schedules

	Subtrial C	Subtrial B	Subtrial A	Subtrial D
Dose (mg)	160	B-3	A-3	D-3
	120	C-2	A-2	D-2
	90	C-1	B-1	A-1
	3/14 × 2	7/28	14/28	21/28
				Dosing schedule (day/day)

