3.1. Starting Dose in Each Subtrial

The dose of DS-3032b for Cohort 1 in Subtrial A will be 90 mg (see “[Section 5.2.3 Rationale for the Dose and Regimen](#)”).

The starting dose in the subtrial that has a smaller number of dosing days than the subtrial in which the MTD has been determined will be equal to or lower than the MTD in the subtrial in which the MTD has been determined. For instance, when the MTD in Subtrial A is determined to be 120 mg, the starting dose in Subtrial B will be 120 mg or 90 mg.

The starting dose in the subtrial that has a greater number of dosing days than the subtrial in which the MTD has been determined will be lower than the MTD in the subtrial in which the MTD has been determined. For instance, when the MTD in Subtrial A is determined to be 160 mg, the starting dose in Subtrial D will be 120 mg or 90 mg. When the MTD has not been reached in Subtrial A, the starting dose in Subtrial D will be equal to or lower than the maximum dose used in Subtrial A.

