3.2. Explorative Dose Finding in Each Subtrial

After confirming the DLT rate in Cycle 1 in each cohort in accordance with “Section 5.3.1 Definition of Dose-limiting Toxicities,” the dose for the next and subsequent cohorts will be determined, in consideration of the following i) and ii). As a rule, each cohort consists of 3 to 6 subjects, and if “Section 5.4 Enrollment of Additional Subjects” is applicable, enrollment of additional subjects will be considered.

- i) Recommended dose, guided by mCRM using a Bayesian logistic regression model (BLRM) incorporating the EWOC principle
- ii) Clinical evaluation of the toxicological profile and information on pharmacokinetics/pharmacodynamics (PK/PDy)

Rationale:

The study design was selected in reference to the “Guidelines for Clinical Evaluation of Anticancer Drugs.¹⁷” The Bayesian statistical analysis methods are specified in “Section 11.7 Details of Modified Continual Reassessment Method.”

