11.1. General Statistical Considerations

Patients treated with the same dose level and schedule will be pooled into a single treatment group. All statistical analyses will be performed by treatment group, unless otherwise noted. Subjects whose dose is reduced will be analyzed in the dose group before dose reduction.

Baseline values of each subject, unless otherwise specified, will be the last observed values that are available before the first dose of the study drug.

Unless otherwise noted, continuous variables will be summarized by the number of subjects analyzed, arithmetic mean, standard deviation, minimum, median, and maximum, whereas categorical variables will be summarized by frequency and proportion.

Analyses of changes from baseline (eg, absolute change, shift table) will be performed for subjects with the baseline value and at least one value available after treatment. Two-sided 95% confidence interval (CI) will be determined, unless otherwise noted.

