11.4.4. Pharmacokinetic Analysis

Pharmacokinetics will be analyzed for each subtrial in the pharmacokinetic analysis set.

Summary statistics of plasma concentrations of DS-3032a will be calculated by dose at each time point, and a plasma concentration-time profile will be prepared.

For the pharmacokinetic parameters that are calculated by the non-compartmental analysis, summary statistics will be calculated by dose. The relationship between dose and each pharmacokinetic parameter will also be assessed.

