11.7.2. Prior Distribution of Bayesian Logistic Regression Model

Assuming that BLRM model parameters $\log(\alpha)$ and $\log(\beta)$ follow bivariate normal distribution, a minimally informative prior distribution is set as follows. If other dosing schedules are assessed, each parameter will be set separately based on the information obtained up to that time.

Parameter	Mean	Standard Deviation	Correlation Coefficient
$\log(\alpha), \log(\beta)$	(-1.8999, 1.3484)	(2.2792, 1.3727)	-0.3157

The above parameters for a prior distribution will be calculated as shown below.

- Based on the overseas Phase 1 study (U102), the median probability of the DLT rate was estimated to be 5% and 20% for the 120 mg qd 21/28 day schedule and the 160 mg qd 21/28 day schedule, respectively.
- From the ratio (0.67) of the dosing days in this study to U102, the median probability of the DLT rate is assumed to be 3% and 13% at doses of 120 mg and 160 mg, respectively, in this study.
- Based on the median probability of the DLT rate at the above doses, parameters of the bivariate normal distribution will be calculated to generate vague prior Bayesian intervals (to minimize prior information) using minimal information beta distribution.

11.7.3. Recommended Dose for the Next Cohort by Bayesian Logistic Regression Model Incorporating the Escalation with Overdose Control Principle

The recommended dose in the next cohort is decided based on posterior distribution of the DLT rate at planned doses (90 mg, 120 mg, and 160 mg). After completing DLT evaluation in 3 subjects per cohort in principle, posterior distribution of the DLT rate at each planned dose will be estimated using BLRM based on the results of DLT evaluation and prior distribution set in “[Section 11.7.2 Prior Distribution of Bayesian Logistic Regression Model](#),” and posterior probability of the DLT rate falling under the following four intervals will then be calculated for each planned dose. The following posterior probabilities can also be calculated for other doses than the planned, as long as the dose is more than 1.3 times but not more than 2 times of the dose in the concerned cohort.

- [0, 16%]: DLT rate interval for under-dosing
- (16, 33%]: target DLT rate interval
- (33, 60%]: DLT rate interval for excessive toxicity
- (60, 100%]: DLT rate interval for unacceptable toxicity

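### If a second subtrial reuses a dose, the by-subtrial PK rule splits first-dose (C1D1) data collected under the same conditions; an additional pooled C1D1 summary would be more precise at almost no cost

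*Combined protocol and SAP*

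**What the plan says.** Section 11.4.4 sets the rule: "Pharmacokinetics will be analyzed for each subtrial in the pharmacokinetic analysis set". Within it, "Summary statistics of plasma concentrations of DS-3032a will be calculated by dose at each time point", non-compartmental parameters are also summarised by dose, and the relationship between dose and each parameter is assessed. The synopsis gives the same by-subtrial rule: "Pharmacokinetics will be analyzed for each subtrial". Section 11.1 groups in the same way for analyses in general: "Patients treated with the same dose level and schedule will be pooled into a single treatment group".

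Three features of the design bear on this:

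- **Subtrials B to D are conditional.** Section 3: "The study will be started from Subtrial A, and other subtrials will be conducted as necessary".
- **Doses can overlap.** Section 3.1 gives the example of an MTD of 120 mg in Subtrial A, in which case "the starting dose in Subtrial B will be 120 mg or 90 mg". Figure 3.1 places the subtrials on a common grid of 90, 120 and 160 mg.
- **Groups are small.** Section 3.2: "As a rule, each cohort consists of 3 to 6 subjects".

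Section 7 lists the C1D1 parameters with no adjustment by subtrial. Only the second PK day is re-read: Day 14 in A becomes Day 7 in B, Day 3 in C and Day 15 in D.

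**The concern.** First-dose PK comes before any divergence of the schedules. A subject on 120 mg in Subtrial A and one on 120 mg in Subtrial B are under the same conditions until after the Day 2 pre-dose sample. Grouping by schedule is natural for the second PK day, but it has no pharmacological basis for C1D1.

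What is at stake is the precision of a descriptive result. PK is a secondary objective. Under the stated rule, if two subtrials share a dose, the C1D1 tables would give two estimates of one quantity, each from a handful of subjects. The C1D1 dose-PK relationship would likewise be assessed within each subtrial, not on all subjects who contribute to it.

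**Working it through.** **1. Are the C1D1 data comparable across subtrials?** Table 6.7.1 gives the sampling up to the second dose:

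| Subtrial | Day 1 samples | Next sample | Second PK day |
|---|---|---|---|
| A | pre-dose, 1, 2, 3, 6, 8 h | Day 2 pre-dose | Day 14 |
| B | same | Day 2 pre-dose | Day 7 |
| C | same | Day 2 pre-dose | Day 3 |
| D | same | Day 2 pre-dose | Day 15 |

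All four schedules dose once daily from Day 1 (Section 3). C1D1 conditions are identical. The second PK day is not.

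**2. The plan's own figures.** Section 11.6 gives 9 to 24 subjects. The minimum is 3 doses × 3 = 9 in Subtrial A alone, and the worked example is 3 × 6 = 18. Both reproduce. If 24 is read as a ceiling over all subtrials, 24 − 9 = 15 or 24 − 18 = 6 subjects remain for a further schedule. No precision figure for PK is stated, so there is none to reproduce.

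**3. Gain from pooling.** For log-normal exposure with between-subject coefficient of variation CV:

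- SD of log exposure: s = √ln(1 + CV²)
- SE of the log mean: s/√n
- 95% CI of the geometric mean: estimate ×/÷ exp(t(0.975, n−1) × s/√n)

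Pooling k equal subtrials multiplies the SE by 1/√k. For k = 2 this is 0.71, a reduction of 29%, whatever the CV. For k = 4 it is 0.50.

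The documents mention inter-subject variability in exposure (Section 5.2.1) but give no value, so CV is assumed. At CV 50%, s = √ln(1.25) = 0.472:

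- n = 3: exp(4.303 × 0.273) = 3.23
- n = 6: exp(2.571 × 0.193) = 1.64
- n = 12: exp(2.201 × 0.136) = 1.35

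95% CI factors over the assumed range:

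| Assumed CV | n = 3 | n = 6 | n = 12 |
|---|---|---|---|
| 30% | 2.07 | 1.36 | 1.21 |
| 50% | 3.23 | 1.64 | 1.35 |
| 70% | 4.80 | 1.94 | 1.49 |

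**4. How much of the fall is information?** Going from 3 to 6 subjects, the SE falls by 29%. The rest of the narrowing comes from the t quantile, which drops from 4.303 (2 df) to 2.571 (5 df). Going from 6 to 12 it moves only from 2.571 to 2.201, so the narrowing is mostly the SE.

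**5. Against the dose step.** The planned step is 120/90 = 160/120 = 1.33. Pooled n = 6 gives 1.36 to 1.94, still wider than one step. Pooled n = 12 is narrower only at CV 30% (1.21). Pooling helps but does not make the C1D1 estimates sharp.

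**The case against.** The case for leaving the plan alone has real substance.

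- **The loss is conditional.** A second subtrial must open and must reuse a dose. The Section 3.1 doses are examples, and Section 11.7.3 lets other doses be evaluated. This version is dated 7 October 2019 and the planned period ends on 31 December 2019: 85 days, about 12 weeks, against a 28-day DLT period per cohort. The documents do not say whether another subtrial had opened. This stands and limits the point.
- **Two groups of 3 is the most favourable case.** A likely shared dose is the Subtrial A MTD, and two of the four completion criteria in Section 5.3.2 require at least 6 evaluated subjects at the selected dose. The step from 6 to 12 (1.64 to 1.35 at CV 50%) is then the fairer guide. This stands.
- **By-subtrial tables have a purpose.** The second PK day differs by schedule, and the accumulation ratio relates it to Day 1. The subtrials are not randomised, and Subtrial A comes first, so separate display lets a reader see cohort differences. This stands, and it is why the pooled table should be added and not substituted.
- **Other routes exist.** Section 11.4.6 foresees population PK modelling with no restriction to one subtrial, and Section 11 refers further detail to a separate Statistical Analysis Plan. This stands only in part: the modelling is optional and reported separately, and deferring detail does not override a by-subtrial rule already stated.

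A reader might infer that the plan ignores data it holds. The documents do not support that: all data are collected, kept and summarised, and modelling could use them together. A reader might also infer that dose or MTD decisions suffer. Sections 3.2 and 5.3.2 bring PK into a comprehensive evaluation, and nothing confines that evaluation to by-subtrial tables. No decision is shown to change.

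**Conclusion.** The point holds as a conditional, optional gain in efficiency. The by-subtrial rule suits multiple-dose PK but not C1D1. Where two equal subtrials share a dose, pooling reduces the SE of the log mean by 29%; the narrowing of the interval depends on group size and CV, as tabulated above. With Subtrial A alone the gain is zero.

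The conclusion rests on three assumptions: log-normal exposure, a between-subject CV of 30% to 70% that the documents do not supply, and no systematic difference on Day 1 between subjects enrolled in different subtrials at the same dose. The geometric-mean interval is used here as a yardstick. Section 11.1 prescribes arithmetic summaries by default, and the SE of an arithmetic mean falls by the same 29% for the same pooling. The summaries are descriptive, with no precision target and no sample size resting on them, so this is not an error in the plan.

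**What to change.** Add to Section 11.4.4 and to the pharmacokinetic paragraph of the synopsis:

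> If more than one subtrial is conducted, C1D1 concentrations and parameters will additionally be summarised by dose pooled over subtrials, and the dose-PK relationship for C1D1 parameters will be assessed on the pooled data; by-subtrial summaries are retained, and multiple-dose parameters are analysed by subtrial.

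The cost is one sentence in each place and one extra table, produced only if a second subtrial opens. It needs no new samples, visits or subjects, and it leaves the dose-finding model unchanged.
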